1.0 Objectives

- 1.1 Primary Objective
- To assess the time to progression (TTP) in patients with HCC treated FOLFOX-S.
- 1.2 Secondary Ojective
 - To evaluate the tolerability and toxicities of FOLFOX-S regimen in this population of patients.
 - To assess the response rate, the duration of response, median PFS, and median OS of FOLFOX-S in patients with HCC.

• To assess changes of angiogenic and inflammatory parameters with treatment of sorafenib.

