S-FOLFOX in HCC

Yes: New lesions are present. Note: If new lesions are present, the patient is considered to have progressive disease overall.

Overall Response

Overall response will be determined as tabulated below, based on the evaluation of target, non-target, and new lesions:

Target lesions	Non-Target lesions	New Lesions	Overall response
CR	CR	No	CR
CR	Incomplete response/SD	No	PR
PR	Non-PD	No	PR
SD	Non-PD	No	SD
PD	Any	Yes or No	PD
Any	PD	Yes or No	PD
Any	Any	Yes	PD

To be assigned a status of PR or CR, changes in tumor measurements must be confirmed by repeat assessments that should be performed no less than 4 weeks after the criteria for response are first met. Longer intervals as determined by the study protocol may also be appropriate.

In the case of SD, follow-up measurements must have met the SD criteria at least once after study entry at a minimum interval (in general, not less than 6-8 weeks) that is defined in the study protocol.

Every effort should be made to document tumor measurements and extent of disease, even after discontinuation of therapy, in order to classify patients for overall response as described above. Patients who do not have tumor response assessment due to rapid progression or toxicity will be considered as non-responders, will be included in the denominator for the response rate, and will be classified into one of the following categories:

- death attributed to disease progression
- deterioration attributed to disease progression
- death attributed to drug toxicity
- early discontinuation attributed to drug toxicity

Note: If a patient receives subsequent therapy before tumor progression is documented, the reason for changing therapy must be reported; reasons

include clinical progression, drug toxicity, or secondary therapy for maintenance of tumor response.

Duration of Overall Response

The duration of overall response is measured from the time measurement criteria are met for CR or PR (whichever status is recorded first) until the first date that recurrence or PD is objectively documented, taking as reference for PD the smallest measurements recorded since the treatment started. Patients who do not relapse will be censored at the day of their last tumor assessment.

Time to response

Time from date of initial treatment until first objective documentation of response.

Time to tumor progression

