Time from date of initial treatment to first objective documentation of progressive disease or death. Patients who die without a reported prior progression will be considered to have progressed on the day of their death.

Time to treatment failure

Time from date of initial treatment to first objective documentation of progressive disease, or off study date, whichever occurs first.

Time to death

Time from date of initial treatment to date of death

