14.2.2 Secondary Efficacy Variables

The secondary objectives are to assess the toxicity profiles of this regimen and the preliminary data on response rate and overall survival. Overall survival is defined as the time from study entry until death from any cause. Overall survival will be calculated using the Kaplan-Meier method, and confidence limits for survival estimates will be calculated using the Greenwood formula. Progression free survival is defined as the time from study entry until disease progression or death from any cause. Response rate is defined as the percentage of patients achieving either CR or PR. Duration of response is defined as the time interval from the initial response to the time disease progression is observed.

All categories of toxicity and complications of the treatment will be recorded. Toxicity and complications of the treatment will be assessed based on reports of adverse events, physical examinations, and laboratory measurements.

REFERENCES/BIBLIOGRAPHY

3. Llovet JM, Bruix J: Molecular targeted therapies in hepatocellular carcinoma. Hepatology 48:1312-27, 2008

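### Read literally, duration of response censors a responder who dies without documented progression, while TTP and PFS count the same death as an event

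*Combined protocol and SAP*

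**What the plan says.** Duration of response is a secondary objective (Section 1.2): "To assess the response rate, the duration of response, median PFS, and median OS of FOLFOX-S in patients with HCC". It is defined twice.

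- Section 10.2, Duration of Overall Response, runs from the first CR or PR "until the first date that recurrence or PD is objectively documented". It then gives the censoring rule: "Patients who do not relapse will be censored at the day of their last tumor assessment". There is no exception for patients who have died.
- Section 14.2.2: "Duration of response is defined as the time interval from the initial response to the time disease progression is observed". Death is again not named.

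Two other endpoints handle death explicitly.

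- TTP, also in Section 10.2: "Time from date of initial treatment to first objective documentation of progressive disease or death", with the added rule "Patients who die without a reported prior progression will be considered to have progressed on the day of their death".
- PFS, in Section 14.2.2: "Progression free survival is defined as the time from study entry until disease progression or death from any cause".

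Nothing in the plan extends the TTP rule on deaths to duration of response or explains why the endpoints differ.

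**The concern.** A responder who dies between scans has not relapsed in the sense of Section 10.2, so the censoring rule applies. The response then counts as ongoing at the last scan, and a Kaplan-Meier estimate treats the patient as someone who would have gone on responding like those still followed. TTP and PFS record the same death as a failure.

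At stake is how a reader understands the durability of response. A duration that leaves deaths out looks equal to or longer than one that counts them. A reader who sees PFS and duration of response side by side would probably assume that both treat death alike. Few responders are expected, so the handling of one or two patients could shift the reported figure.

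**Working it through.** **1. The definitions side by side**

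| Endpoint | Section | Ends at | Responder who dies without documented progression |
|---|---|---|---|
| Duration of response | 10.2 | Documented recurrence or progression | Censored at last tumor assessment |
| Duration of response | 14.2.2 | Observed progression | Not named; no event |
| TTP | 10.2 | Progression or death | Event on the day of death |
| PFS | 14.2.2 | Progression or death from any cause | Event |

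The two definitions of duration of response agree with each other. The difference is across endpoints.

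**2. The plan's own figure**

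The plan gives no figure for duration of response. Its only design figure (Section 14.2.1) is for TTP: 40 patients, 80% power, median 5 against 7 months, one-sided 10%, with 18 months of accrual and 24 of follow-up.

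- Events needed: (1.282 + 0.842)² / ln(7/5)² = 39.8.
- Probability of an event under the alternative: 0.957, so N = 39.8 / 0.957 = 41.6.
- Power with 40 patients: 78.8% at the expected 38.3 events (40 × 0.957) and 80.1% at 40 events.

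The stated design is reproduced closely, and duration of response plays no part in it.

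**3. Direction**

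Let Λ_P(t) and Λ_D(t) be the cumulative hazards, among responders, of documented progression and of death without it. Censoring deaths targets exp(−Λ_P(t)). Counting them targets exp(−Λ_P(t) − Λ_D(t)), which is never larger. The duration estimated under the literal rule is therefore equal or longer.

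One qualification applies to small samples. The ordering holds exactly when scans fall on common dates. Because the rule censors at the last scan and not at death, visit windows could allow a small local exception if another responder progresses between that scan and the death.

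**4. Size**

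Assume independent constant hazards λ_P and λ_D, and let p = λ_D / (λ_P + λ_D) be the share of responses that end in death without documented progression. The medians are ln 2 / λ_P (deaths censored) and ln 2 / (λ_P + λ_D) (deaths counted), so their ratio is 1 / (1 − p). The documents do not give p, so it is varied. The last column assumes a median of 5.5 months to progression or death; the plan gives no such figure for responders.

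| p | 1 / (1 − p) | Median longer by | Median with deaths censored |
|---|---|---|---|
| 0% | 1.00 | 0% | 5.5 months |
| 10% | 1.11 | 11% | 6.1 months |
| 20% | 1.25 | 25% | 6.9 months |
| 30% | 1.43 | 43% | 7.9 months |

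**5. Number of responders**

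Using response rates cited in Sections 2.2 and 2.4:

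- FOLFOX4, 8.2%: 40 × 0.082 = 3.3
- sorafenib with XELOX, 14%: 40 × 0.14 = 5.6
- GEMOX, 18%: 40 × 0.18 = 7.2

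That is about 3 to 7.

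**6. Small-sample check**

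Samples of 6 responders were simulated with 8-weekly scans (Study Calendar) on common dates and the same assumed 5.5-month median, 4,000 runs per share. Each sample was analysed by Kaplan-Meier both ways.

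| p | Median longer with deaths censored | Median equal | Median shorter |
|---|---|---|---|
| 0% | 0% | 100% | 0% |
| 10% | 24% | 76% | 0% |
| 20% | 46% | 54% | 0% |
| 30% | 58% | 42% | 0% |

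A share of 20% to 30% of 6 is 1.2 to 1.8 deaths. In large simulated samples, the estimated proportion still in response at 6 months rose from about 0.49 to 0.53, 0.57 and 0.60 at shares of 10%, 20% and 30%.

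**The case against.** The case for leaving the text alone is substantial.

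- **It is a legitimate estimand.** A progression-only duration answers a different question from a progression-or-death duration. A reader might take the 11%, 25% and 43% as a measured bias from informative censoring. They are not: under independent constant hazards, censoring deaths recovers the progression-only distribution apart from scan timing, so the percentages are the gap between two estimands. If death and progression are dependent, 1 / (1 − p) need not hold.
- **The objective does not name a median.** In Section 1.2 the word median is attached to PFS and OS, not to duration of response. Section 14.2.2 names Kaplan-Meier only for OS. A reader might infer that a stated objective, median duration of response, is distorted; the text does not go that far.
- **The dates differ.** A reader might infer that one patient has a TTP event and a censored response on the same day. In general that is not so: the TTP event falls on the day of death, and censoring falls at the last scan, which can be weeks earlier.
- **It is not a contradiction within one endpoint.** The mismatch could equally be traced to TTP, whose inclusion of death gives it the same kinds of event as PFS.
- **Such deaths may be rare.** Eligibility requires no cirrhosis or Child-Pugh A, ECOG 0 or 1, a life expectancy of at least 12 weeks and a CLIP score of at most 3. Responses must be confirmed at least 4 weeks later, and Section 10.2 asks for tumor measurements to be sought even after therapy stops.

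All of this limits the point without removing it. The plan does not say that a progression-only estimand was chosen, and it does not warn that deaths are treated differently from TTP and PFS. If the text is read instead as silent on death, the rule for these patients is undefined and would have to be chosen once the data are in hand. Both readings need a clarification.

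**Conclusion.** The point holds as a minor one. Followed literally, the rule censors at the last scan any responder who dies without documented progression, although TTP and PFS count that death, and the plan gives no reason. Compared with a progression-or-death definition, the duration estimated can only be equal or longer.

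How much longer cannot be derived from the documents. The range of 0% to 43% rests on assumed shares of 0% to 30%, on independent constant hazards and on a median being reported. If no responder dies without documented progression, there is no effect.

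A reader might infer that the efficacy conclusion is at risk. The documents do not support that. Duration of response is secondary and has no role in the sample size or the primary test, and the deaths in question still count in TTP, PFS and OS.

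**What to change.** In Sections 10.2 and 14.2.2, define duration of response as the time from first documentation of CR or PR to the earlier of documented progression or death from any cause. Censor at the last tumor assessment only patients who are alive without progression.

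If a progression-only duration is wanted, say so in both places, give the reason, and add a sensitivity analysis that counts deaths without documented progression as events.

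The cost is about one sentence in each section, with no additional data and no change to the sample size. The downside is that the reported duration may be shorter. Under the assumptions above, moving from the literal rule to the proposed one multiplies the median by 1 − p, a reduction of 10%, 20% or 30% at those shares.

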11.0 REPORTING OF ADVERSE EVENTS

11.1Adverse Event and Reporting Definitions (CTCAE version 4.0)

In the event of an adverse event, the first concern will be for the safety of the subject. Investigators are required to report to Bayer Drug Safety any **serious adverse event**, whether **expected** or **unexpected**, and which is assessed by the investigator to be **reasonably or possibly related** to or caused by sorafenib. All events meeting these criteria will be reported for the time period beginning with any amount of exposure to sorafenib through the protocol-defined follow-up period. Serious criteria, definitions, and guidance for reporting follow.

An **adverse event (AE)** is any untoward medical occurrence in a subject participating in an investigational study or protocol regardless of causality assessment. An adverse event can be an unfavorable and unintended sign (including an abnormal laboratory finding), symptom, syndrome or disease associated with or occurring during the use of an investigational product whether or not considered related to the investigational product. Serious adverse events (SAE) are adverse events occurring at any dose which meet one or more of the following serious criteria:

• Results in **death** (i.e. the AE caused or lead to death)

• Is **life-threatening** (i.e. the AE placed the subject at immediate risk of death; it does not apply to an AE which hypothetically might have caused the death if it were more severe)

• Requires or prolongs inpatient **hospitalization** (i.e. the AE required at least a 24-hour inpatient hospitalization or prolonged a hospitalization beyond the expected length of stay; hospitalizations for elective medical/surgical procedures, scheduled treatments, or routine check-ups are not SAEs by this criterion)

- Is **disabling** (i.e. the AE resulted in a substantial disruption of the subject's ability to carry out normal life functions)
- Is a **congenital anomaly/birth defect** (i.e., an adverse outcome in a child or fetus of a subject exposed to the study drug prior to conception or during pregnancy)

• It does not meet any of the above serious criteria but **may jeopardize the subject** and **may require medical or surgical intervention** to prevent one of the outcomes listed above

Expected adverse events are those adverse events that are **listed** or characterized in the Package Insert or current Investigator Brochure.

Unexpected adverse events are those **not listed** in the Package Insert (P.I.) or current Investigator Brochure (I.B.) or not identified. This includes adverse events for which the specificity or severity is not consistent with the description in the P.I. or I.B. For example, under this definition, hepatic necrosis would be unexpected if the P.I. or I.B. only referred to elevated hepatic enzymes or hepatitis.

11.2 Reporting of Serious Adverse Events

Each serious adverse event must be followed up until resolution or stabilization, by submission of updated reports to the designated person. An isolated laboratory abnormality that is assigned grade 4, according to CTC definition, is not reportable as an SAE; unless the investigator assesses that the event meets standard ICH criteria for an SAE. CTC grade 4 baseline laboratory abnormalities that are part of the disease profile should not be reported as an SAE, specifically when they are allowed or not excluded by the protocol inclusion/exclusion criteria.

When required, and according to local law and regulations, serious adverse events must be reported to the Ethics Committee and Regulatory Authorities.

All serious adverse events should be reported to Bayer within 24 hours. In the event of such an event, the investigator should refer to the Pharmacovigilance section of the contract for reporting procedures.

The Investigator may report serious adverse drug reactions (SADRs) using either:

An ADEERS form (Adverse Event Expedited Reporting System) available at http://ctep.cancer.gov/reporting/adeers.html

OR

A MedWatch form available at http://www.fda.gov/medwatch/

All reports shall be sent electronically to:

Electronic Mailbo	DX:
Facsimile:	
Address: Mail only:	Global Pharmacovigilance - USA Ba yer HealthCare Pharmaceuticals Inc.
Address:	
Reports for all Communications	Bayer products can also be phoned in via our Clinical s Dept:

Phone:

AND:

Dana Farber Cancer Institute IRB/ OHRS [name]

Phone:	
Fax:	

MedWatch 3500 Reporting Guidelines:

In addition to completing appropriate patient demographic and suspect medication information, the report should include the following information within the Event Description (section 5) of the MedWatch 3500 form:

- Protocol description (and number, if assigned)
- Description of event, severity, treatment, and outcome if known
- Supportive laboratory results and diagnostics

• Investigator's assessment of the relationship of the adverse event to each investigational product and suspect medication

Follow-up information:

Additional information may be added to a previously submitted report by any of the following methods:

• Adding to the original MedWatch 3500 report and submitting it as follow-up

• Adding supplemental summary information and submitting it as follow-up with the original MedWatch 3500 form

• Summarizing new information and faxing it with a cover letter including subject identifiers (i.e. D.O.B. initial, subject number), protocol description and number, if assigned, brief adverse event description, and notation that additional or follow-up information is being submitted (The patient identifiers are important so that the new information is added to the correct initial report)

Occasionally Bayer may contact the reporter for additional information, clarification, or current status of the subject for whom and adverse event was reported. For questions regarding SAE reporting, you may contact the Bayer Drug Safety representative noted above.

Study Drug Relationship:

The investigator will determine which events are associated with the use of study drug. For reporting purposes, an AE should be regarded as possibly related to the use of the investigational product if the investigator believes:

• There is a clinically plausible time sequence between onset of the AE and sorafenib administration; and/or

• There is a biologically plausible mechanism for sorafenib causing or contributing to the AE; and

• The AE cannot be attributed solely to concurrent/underlying illness, other drugs, or procedures.

Follow-up Reports

- The Investigator should take all appropriate measures to ensure the safety of the patients, notably he/she should follow up the outcome of any Serious Adverse Event submitted to the FDA on a 3500 form and complete follow-up forms as necessary. The patient must be followed up until clinical recovery is complete and/or laboratory results have returned to normal. This may mean that follow-up will continue after the patient has completed the trial and that additional investigations may be necessary.
- Any reportable Serious Adverse Events brought to the attention of the Investigator at any time after cessation of the trial and considered by him/her to be reasonably associated with medication administered during the period should also be submitted to the FDA. As for initial reports, a copy is to be provided to Sanofi-Synthelabo New York Safety Surveillance or the appropriate manufacturer of the product. within 24 hours after FDA submission (see above)
- The 3500 form providing follow-up information about a reportable SAE must be submitted to the FDA as soon as possible or within 15 calendar days.
- As with the initial submission to the FDA of the 3500 form, the principal investigator is also responsible for providing all follow-ups for reportable Serious Adverse Events (on form 3500) to the IRB and co/sub-investigators (Dear Investigator Letter) participating on this protocol.

IND Annual Report

The principal investigator is responsible for preparing and submitting the IND annual reports to the FDA (CFR312.33) within 60 days of the anniversary date that the IND went into effect. A copy of the report shall be provided to New York Safety Surveillance within 24 hours of submission to the FDA.

12.0 Data Safety and Monitoring

12.1 Method

The QACT will collect, manage, and monitor data for this study.

12.2 Data Submission

The schedule for completion and submission of case report forms (paper or electronic) to the QACT is as follows:

Form	Submission Timeline		
Eligibility Checklist	Complete prior to registration with QACT		

On Study Form	Within 14 days of registration
Baseline Assessment Form	Within 14 days of registration
Treatment Form	Within 10 days of the last day of the cycle
Adverse Event Report Form	Within 10 days of the last day of the cycle
Response Assessment Form	Within 10 days of the completion of the cycle required for response evaluation
Off Treatment/Off Study Form	Within 14 days of completing treatment or being taken off study for any reason
Follow up/Survival Form	Within 14 days of the protocol defined follow up visit date or call

12.3 Safety Meetings

The DF/HCC Data and Safety Monitoring Committee (DSMC) will review and monitor toxicity and accrual data from this trial. The committee is composed of clinical specialists with experience in oncology and who have no direct relationship with the study. Information that raises any questions about participant safety will be addressed with the Principal Investigator and study team.

The DSMC will meet quarterly and/or more often if required to review toxicity and accrual data. Information to be provided to the committee may include: up-to-date participant accrual; current dose level information; DLT information; all grade 2 or higher unexpected adverse events that have been reported; summary of all deaths occurring within 30 days for Phase I or II protocols; for gene transfer protocols, summary of all deaths while being treated and during active follow-up; any response information; audit results, and a summary provided by the study team. Other information (e.g. scans, laboratory values) will be provided upon request.

12.4 Monitoring

Involvement in this study as a participating investigator implies acceptance of potential audits or inspections, including source data verification, by representatives designated by the DF/HCC Overall Principal Investigator (or Protocol Chair) or DF/HCC. The purpose of these audits or inspections is to examine study-related activities and documents to determine whether these

activities were conducted and data were recorded, analyzed, and accurately reported in accordance with the protocol, institutional policy, Good Clinical Practice (GCP), and any applicable regulatory requirements.

All data will be monitored for timeliness of submission, completeness, and adherence to protocol requirements. Monitoring will begin at the time of participant registration and will continue during protocol performance and completion.

